11.5.2. Severity

The Investigator will use the grading scale in [Table 9](#) to describe the intensity of the AE following general categorical descriptors outlined in the DAIDS table for Grading the Severity of Adult and Pediatric Adverse Events ([DAIDS 2017](#)).

Table 9: Guidelines for Severity Assessments

Grade 1 Mild	Mild symptoms causing no or minimal interference with usual social and functional activities with intervention not indicated
Grade 2 Moderate	Moderate symptoms causing greater than minimal interference with usual social and functional activities with intervention indicated
Grade 3 Severe	Severe symptoms causing inability to perform usual social and functional activities with intervention or hospitalization indicated
Grade 4 Potentially Life Threatening	Potentially life-threatening symptoms causing inability to perform basic self-care functions with intervention indicated to prevent permanent impairment, persistent disability, or death
Grade 5 Death	Fatal

Refer to the [DAIDS table for Grading the Severity of Adult and Pediatric Adverse Events](#) for details regarding event grading.

11.5.3. Serious Adverse Event

Any adverse experience occurring at any dose of study medication that occurs during time periods indicated below are considered serious if they result in any of the outcomes listed in [Section 11.4.4](#).

Cohort	SAE monitoring period from signing of Informed Consent Form:
1A, 1B	Through 4 months after the dose of study drug
2A, 2B, 3A, 3B, 4B	Through 205 days after the last dose of study drug (Day 206 ±10 days)

Hospitalization for a planned or elective procedure or surgery for a pre-existing condition that has not worsened is not considered an SAE.

11.6. Adverse Event Follow Up

All unresolved SAEs and study drug-related AEs will be followed by the study staff until resolution or deemed stable, regardless of severity.

11.7. Adverse Event Management

The Investigator should employ best medical judgement in determining how to manage AEs. Any questions regarding AE management should be directed to the Medical Monitor.

11.8. Risks for Women of Childbearing Potential or During Pregnancy

The risks of CD388 Injection in pregnant or lactating/nursing women are unknown. Pregnant or nursing female subjects are excluded from this study.

Subjects must be instructed to inform the Investigator immediately if they or their partner becomes pregnant during the study. In the case of a partner pregnancy, partner informed consent must be attained prior to collecting information related to the pregnancy and to allow the Investigator to follow them for the outcome of the pregnancy. In the event of a confirmed pregnancy, the following actions should be taken:

- The pregnancy should be reported to the Sponsor within 24 hours of the subject notifying the Investigator using the applicable Pregnancy Report Form.
- The Investigator should counsel female subjects regarding the possible effects of CD388 Injection exposure on the fetus and the need to inform the study site of the outcome of the pregnancy.
- The subject or subject's partner, if consented, should be monitored until the postnatal day 28 or until termination of the pregnancy. The outcome should be reported using the Pregnancy Outcome or Abnormal Pregnancy Outcome form.

Pregnancy is not an AE, in and of itself. However, any pregnancy complication or elective termination of a pregnancy for medical reasons will be recorded as an AE or SAE.

A spontaneous abortion is always considered an SAE and will be reported as described in the AE and SAE sections. Furthermore, any SAE occurring as an adverse pregnancy outcome post-study must be reported to the Medical Monitor.

12. STATISTICAL METHODS

A Statistical Analysis Plan (SAP) will be prepared and finalized before unblinding for the first interim analysis. Any deviations from the final SAP will be described and justified in the study report. All statistical analyses will be performed using SAS®.

Descriptive statistics, including the numbers and percentages for categorical variables, and the numbers, means, standard deviations, medians, minimums, and maximums for continuous variables, will be provided. All data will be summarized separately by dose level, route (IM or SQ), and study drug (CD388 Injection or placebo). Listings of individual subject data will also be produced.

Safety, PK, and pharmacodynamics will be summarized using descriptive statistics. There will be no formal hypothesis testing.

12.1. Analysis Populations

Analysis populations are:

- Safety Population: all subjects who receive any amount of study drug
- PK Analysis Population: all subjects who receive CD388 Injection and who have any blood samples analyzed

12.2. Analysis of Study Population and Subject Characteristics

Demographics (including age, race, ethnicity, and gender), baseline assessments (including height, weight, and BMI), medical history, and administration of study drug will be summarized for the Safety Population.

12.3. Safety Analyses

Safety will be evaluated by presenting summaries of AEs and SAEs, ECGs, clinical laboratory evaluations (hematology, coagulation, serum chemistry, and urinalysis), and vital signs. Adverse events will be coded using the Medical Dictionary for Regulatory Activities (MedDRA). The incidence of TEAEs and AESIs will be presented by System Organ Class (SOC) and Preferred Term (PT), relationship to study drug, severity, and route of administration. Treatment-emergent adverse events are defined as follows:

Cohort	TEAE is an AE that occurs during or after study drug administration:
1A, 1B	Through 4 months after the dose of study drug
2A, 2B, 3A, 3B, 4B	Through 205 days after the last dose of study drug (Day 206 ±10 days)

In addition, the incidence of serious TEAEs and TEAEs leading to discontinuation of study drug or from the study will be presented by SOC and PT. The TEAEs occurring after the first single dose and after the second single dose will be analyzed separately.

Descriptive statistics for clinical laboratory test results, ECG parameters, and vital signs, and for changes from Baseline, will be presented by time point. The incidences of potentially clinically

significant (PCS) clinical laboratory results, ECG parameters, and vital signs will also be summarized by time point.

A summary of the injection site evaluation will be presented. The number and percentage of subjects with any local reaction will be provided as will the number and percentage of subjects with pain, tenderness, erythema/redness, and induration/swelling. The severity of each local reaction will also be presented.

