Subjects in Cohorts 2A and 2B and Cohorts 3A and 3B will receive a second single dose of CD388 Injection or placebo after washout of 3 months or 5 effective half-lives, whichever is longer, after the first dose if it is determined that the safety and tolerability of the first dose is acceptable upon review of the cumulative safety data. Immediately prior to the second single dose, within each dose and route, any dropouts in the sentinel groups will be randomly replaced with subjects from the main groups, retaining their original treatment assignment (i.e., subjects assigned to placebo will remain placebo, and subjects assigned to CD388 will remain CD388; this may require unblinded personnel to oversee).

The PI and Sponsor will review blinded safety data after the initial sentinel group subjects at a dose level have completed dosing and followed for the minimum observation period as determined during the first single dose. If no drug-related SAEs or drug related Grade ≥ 3 AEs have occurred, the subjects in the corresponding main group may be dosed within 24 hours.

The dose escalation scheme is presented in [Section 1.2](#).

The Schedule of Events is presented in [Table 1](#) (first single dose, Cohorts 1A, 1B, 2A, 2B, 3A, 3B), [Table 2](#) (second single dose, Cohorts 2A, 2B, 3A, 3B), and [Table 3](#) (single dose, Cohort 4B). All subjects will be admitted to the clinical research unit (CRU) for observation and safety assessments from Day -1 (check-in) to Day 30.

Subjects will be monitored for AEs (including reactogenicity/injection site reactions and hypersensitivity reactions) and SAEs as indicated below:

Cohort	AE/SAE monitoring period from signing of ICF:
1A, 1B	Through 4 months after the dose of study drug
2A, 2B, 3A, 3B, 4B	Through 205 days after the last dose of study drug (Day 206 ±10 days)

Abbreviation: ICF = informed consent form.

Safety will also be assessed by physical examinations, ECGs, vital signs measurements, and laboratory evaluations (hematology, coagulation, serum chemistry, and urinalysis) at various time points during and after the CRU stay. Concomitant medication use will be recorded throughout the study.

Continuous 12-lead digital ECG recording will be performed using a 12-lead Holter ECG monitor as indicated below:

Cohort	Holter Monitoring Period
1A, 1B	1 hour before administration of study drug until 48 hours after dosing
2A, 2B, 3B	1 hour before first administration of study drug until 48 hours after dosing ^a

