- k. At indicated visits, inspection of administration site and surrounding area will be performed twice daily (once between approximately 2–4 hours postdose, and once approximately 8–12 hours postdose), with any abnormal findings reported as AE s. Reactions will be rated according to the scale provided in [Table 7](#).
- l. For Cohorts 1A, 1B, 2A, 2B, 3B: Blood samples for PK analysis will be collected predose (-24 hour window); post-dose at 2, 4, and 12 hours (each \pm 10 minute window); 24 hours (\pm 30 minute window); 48 hours (\pm 1 hour window); 72, 96, 120 hours (each \pm 2 hour window); and Days 7, 9, 11, 14, 21, 30 (each \pm 2 hour window). Postdose samples collected at outpatient CRU visits at OV1, OV2, OV3, and OV4 have the same windows (i.e., in \pm days) as the visits.
For Cohort 3A: Blood samples for PK analysis will be collected predose (-24 hour window); post-dose at 12 and 24 hours (\pm 30 minute window); 48 hours (\pm 1 hour window); 72, 84, 96, 108, 120 hours (each \pm 2 hour window); and Days 7, 9, 11, 14, 21, 30 (each \pm 2 hour window). Postdose samples collected at outpatient CRU visits at OV1, OV2, OV3, and OV4 have the same windows as the visits.
- m. Blood samples for metabolite identification (e.g., free zanamivir, zanamivir dimers) and CD388 DAR distribution will be collected on Day 1 at 2 hours postdose, on Day 2 at 24 hours postdose, on Days 14 and 30, and at OV3. Urine samples for metabolite identification will be collected on Day 1 from 0–12 hours and from 12–24 hours postdose, on Day 2 from 24–48 hours postdose, on Day 14 over a 24-hour period, and over a 24-hour period that starts on Day 29 and ends prior to CRU check-out on Day 30.
- n. Serum samples for CD388 glycoforms will be collected predose on Day 1 and once in the morning on Days 2, 7, 14, 21, and 30, and at the OV1 and OV3 visits.
- o. A mandatory pharmacogenomic (DNA) blood sample will be collected once, preferably on Day 1 (collection at another time point is allowed if necessary) to allow for pharmacogenomic research related to CD388.
- p. Nasopharyngeal swab samples will be collected predose on Day 1, and on Days 2, 5, 7, 9, 11, 14, 21, and 30.
- q. Adverse events (including influenza-like illness which will be tested for both COVID-19 and flu) will be collected for all subjects from the time of signing the ICF through 4 months after the last dose of study drug, whichever is longer.

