Subjects in Cohorts 2A and 2B and Cohorts 3A and 3B will receive a second single dose of CD388 Injection or placebo after washout of 5 effective half-lives after the first dose if it is determined that the safety and tolerability of the first dose is acceptable upon review of the cumulative safety data. Immediately prior to the second single dose, within each dose and route, any dropouts in the sentinel groups will be randomly replaced with subjects from the main groups, retaining their original treatment assignment (i.e., subjects assigned to placebo will remain placebo, and subjects assigned to CD388 will remain CD388; this may require unblinded personnel to oversee).

The PI and Sponsor will review blinded safety data after the initial sentinel group subjects at a dose level have completed dosing and followed for the minimum observation period as determined during the first single dose. If no drug-related SAEs or drug-related Grade ≥ 3 AEs have occurred, the subjects in the corresponding main group may be dosed within 24 hours.

The dose escalation scheme is presented in [Section 1.2](#).

The Schedule of Events is presented in [Table 1](#) (first single dose, Cohorts 1A, 1B, 2A, 2B, 3A, 3B), [Table 2](#) (second single dose, Cohorts 2A, 2B, 3A, and 3B), and [Table 3](#) (single dose, Cohort 4B). All subjects will be admitted to the clinical research unit (CRU) for observation and safety assessments from Day -1 (check-in) to Day 30. Subjects will be monitored for AEs (including reactogenicity/injection site reactions and hypersensitivity reactions) and SAEs as indicated below:

Cohort	AE/SAE monitoring period from signing of ICF:
1A, 1B	Through 4 months after the dose of study drug
2A, 2B, 3A, 3B, 4B	Through 205 days after the last dose of study drug (Day 206 ±10 days)

Abbreviation: ICF = informed consent form.

Safety will also be assessed by physical examinations, ECGs, vital signs measurements, and laboratory evaluations (hematology, coagulation, serum chemistry, and urinalysis) at various time points during and after the CRU stay. Concomitant medication use will be recorded throughout the study.

Continuous 12-lead digital ECG recording will be performed using a 12-lead Holter ECG monitor as indicated below:

Cohort	Holter Monitoring Period
1A, 1B	1 hour before administration of study drug until 48 hours after dosing
2A, 2B, 3B	1 hour before first administration of study drug until 48 hours after dosing ^a

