7. A positive result at screening or CRU check-in for severe acute respiratory syndrome coronavirus 2 (SARS-CoV-2) by polymerase chain reaction (PCR). Beginning with Protocol Amendment 2, antigen testing may be used if PCR is not available.
8. Unwilling to comply with local health policy effective at the time regarding coronavirus disease 2019 (COVID-19).*
9. Women who are pregnant or nursing.
10. Received any over-the-counter (OTC) medications or nutritional supplements within 7 days, or any prescription medications within 14 days or <5 half-lives prior to dosing.
11. Current nicotine user or has quit habitual nicotine use in the 30 days prior to screening.
12. Received any vaccines or immunoglobulins within 28 days prior to dosing (90 days in case of intravenous immunoglobulin [IVIg] or biologics, or 14 days for COVID-19 vaccine).**
13. Donated blood (within 56 days of screening) or plasma (within 7 days of screening) or experienced significant blood loss or significant blood draw when participating in non-interventional clinical trials within 60 days prior to dosing.
14. Received a blood transfusion within 28 days prior to dosing.
15. Received any biologics within 90 days prior to dosing. Previous participation in another study within 30 days or 5 half-lives of the study drug, whichever is longer, prior to screening; prior participation at any time in non-invasive methodology trials in which no drugs were given is acceptable.
16. The PI considers that the volunteer should not participate in the study.

* Full COVID-19 vaccination prior to participation is strongly recommended.

** In the event a subject chooses to receive one of the two 2-dose approved or emergency-use-authorized COVID-19 vaccines (Comirnaty® [Pfizer], Spikevax™ [Moderna]) in the interval between two CRU stays (Cohort 2A/2B or Cohort 3A/3B), flexibility in timing of the second CRU stay should be applied, to allow appropriate receipt of the second vaccine dosage or booster (based on the respective vaccine label) + 14 days, to minimize risk of confounding findings/observations.

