7.4. Subject Withdrawal Criteria

7.4.1. Subject Stopping Rules

Subjects in Cohorts 2A, 2B, 3A, and 3B will be followed through Outpatient Visit 4 (OV4) of the first dosing period, and will not receive the second single dose:

- If the subject develops anaphylaxis or a related Grade 3 or Grade 4 AE
- If the subject has a persistent (i.e., >5 days with no response to treatment) Grade ≥ 2 rash considered related to the investigational drug by the Principal Investigator ([Appendix 4](#))
- If the Investigator believes that it is in the best interest of the subject to not receive a second dose
- If the subject no longer meets all eligibility criteria prior to the second single dose
- If the subject becomes pregnant prior to the second single dose

If a subject is removed from the study for any reason, the subject will be followed for resolution of any ongoing AE(s).

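### First-dose TEAE tables set about 4 months of counting at 50 mg beside 205 days at 900 mg SQ and a mixed-window placebo column, so late-onset and influenza-like TEAEs at 50 mg are not comparable with the later cohorts

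*Protocol*

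**What the plan says.** Protocol 12.3 gives two TEAE windows. For Cohorts 1A and 1B it is "Through 4 months after the dose of study drug". For 2A, 2B, 3A, 3B and 4B it is "Through 205 days after the last dose of study drug (Day 206 ±10 days" (the closing bracket follows in the source). AE collection is split the same way in Protocol 6.1, 9.10, 11.2 and 11.5.3, so later 50 mg events are not collected. SAP 8.1 defines a TEAE with no end date.

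Protocol 12.3 adds: "The TEAEs occurring after the first single dose and after the second single dose will be analyzed separately". SAP 8 repeats this, and SAP 10.1 counts study days from the relevant dose. The 50 mg and 900 mg groups therefore appear only in the first-dose tables (SAP shells 14.3.1.1, .3, .5, .7, .9, .11 and .13). Those shells show n (%) of the Safety Population by route and dose, beside placebo pooled within route. The note to shell 14.3.1.13 limits influenza-like TEAEs to events collected in the follow-up period. Neither document plans a common cut-off, a person-time rate or a time-to-event summary.

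The second dose at 150 and 450 mg is given "after washout of 3 months or 5 effective half-lives, whichever is longer, after the first dose" in the Synopsis. A later paragraph of Protocol 6.1 says only "after washout of 5 effective half-lives after the first dose". Around COVID-19 vaccination, "flexibility in timing of the second CRU stay should be applied" (Protocol 7.2). Subjects who meet a stopping rule "will be followed through Outpatient Visit 4 (OV4) of the first dosing period, and will not receive the second single dose" (Protocol 7.4.1). Table 1 footnote q, repeated in SAP Appendix A, has AEs collected for all subjects "through 4 months after the last dose of study drug, whichever is longer".

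**The concern.** A crude percentage rises with time at risk. When columns with different counting periods stand side by side, any first onset after about Day 120 can appear at 900 mg but not at 50 mg. A reader can take that for a dose trend. The placebo column does not correct it, because it averages over the same unequal windows and so matches no single dose column.

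TEAE incidence is the primary endpoint, and tables laid out by dose invite reading across. Influenza-like TEAEs are the most exposed, because they are counted only after discharge. For an agent meant to prevent influenza, extra accrual time at the highest dose could hide a favourable trend.

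**Working it through.** **The plan's own count.** Seven cohorts of 2 sentinel + 9 main subjects: 7 × 11 = 77; CD388 7 × 8 = 56; placebo 7 × 3 = 21 (9 IM, 12 SQ). This agrees with Protocol 12.7 and Table 5. The documents give no TEAE rate and no half-life, so both are assumed below.

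**Windows after the first dose**
- 50 mg: 4 months, taken as 120 days. The last scheduled visit is OV4, Day 120 ±14.
- 900 mg SQ: 205 days. Ratio 205/120 = 1.71.
- 150 and 450 mg: up to the second dose. Table 1 sets OV2 to OV4 at about 2, 3 and 4 half-lives, and Table 2 uses Days 84, 126 and 168. If those days rest on the same rule, the half-life is 84/2 = 126/3 = 168/4 = 42 days, and 5 × 42 = 210 days. If the 3-month minimum applied, the window would be about 91 days.

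**50 mg against 900 mg SQ, no drug effect.** Assume the hazard in the first 30 days is k times the later hazard h, and the 50 mg incidence by day 120 is p:
- h = −ln(1 − p)/(30k + 90)
- incidence by day T = 1 − exp(−h(30k + T − 30))

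Example with p = 40%, k = 1: h = 0.5108/120 = 0.004257; incidence by day 205 = 1 − exp(−0.8727) = 58.2%; excess = 8 × (0.582 − 0.400) = 1.5 subjects.

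| Assumed incidence at 50 mg | 900 mg, k = 1 / 4 / 8 | Extra subjects of 8 |
|---|---|---|
| 20% | 32 / 27 / 24% | 0.9 / 0.6 / 0.4 |
| 40% | 58 / 51 / 47% | 1.5 / 0.9 / 0.6 |
| 60% | 79 / 72 / 68% | 1.5 / 1.0 / 0.7 |

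If no first onset falls after Day 120, the excess is 0.

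**150 and 450 mg, constant hazard, 20% at 50 mg.** A 210-day window gives 32.3%, close to the 31.7% at 900 mg. A 91-day window gives 15.6%, so the sign of the difference reverses.

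**Pooled placebo, same rate, second dose at 210 days**
- IM: (3 × 20 + 6 × 32.3)/9 = 28.2%; mean window (3 × 120 + 6 × 210)/9 = 180 days.
- SQ: (3 × 20 + 6 × 32.3 + 3 × 31.7)/12 = 29.1%; mean window (3 × 120 + 6 × 210 + 3 × 205)/12 = 186 days.

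The 50 mg column would show 20% beside these with no drug effect.

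**Influenza-like TEAEs.** Day 30 to Day 120 is 90 days and Day 30 to Day 206 is 176 days, a ratio of 1.96. With a constant rate and no season, 1 − (1 − p)^(176/90) takes 5, 10 and 20% to 9.5, 18.6 and 35.4%. The excess is 0.4, 0.7 and 1.2 subjects of 8.

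**The case against.** The case for leaving the plan alone has weight. Every cohort has the same inpatient stay to Day 30. Escalation rests on at least 14 days of data and the halting rule on 28 days. The analysis is descriptive, with no hypothesis test. Acute and injection-site reactions fall inside every window. The larger excesses need a hazard that stays constant to Day 205 after one dose; with strong front-loading the excess is 0.4 to 0.7 of a subject. Listing 16.2.7.1 gives onset day and time from dosing, so a reader could truncate by hand. All of this stands and limits the consequence. It does not make the printed percentages comparable, and hand truncation does not replace a planned table when one subject of 8 is 12.5 percentage points.

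A reader might infer that every dose above 50 mg is counted for 205 days in these tables, so that no doses can be compared. The documents do not support that. First- and second-dose TEAEs are separated, so the 150 and 450 mg window most naturally closes at the second dose. At the inferred half-life it is close to the 900 mg window, which leaves 50 mg (16 of 56 CD388 subjects) as the odd group.

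A reader might also see a contradiction between follow-up to OV4 in Protocol 7.4.1 and the 205 days in 12.3. That is not clear either: Table 2 ends visits at Day 168 and still takes a final AE assessment by telephone. What is missing is a statement for subjects who never receive a second dose.

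**Conclusion.** The point holds for the first-dose tables and should be addressed. Two parts need no half-life: 50 mg against 900 mg SQ, and the mixed placebo columns. The difference from 150 and 450 mg depends on when the second dose is given, which the documents do not fix, so even its direction is open.

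The excess of about 0.4 to 1.5 subjects of 8 rests on assumed 50 mg incidences of 20 to 60% and an assumed hazard shape; the ratio of windows does not. The harm is confined to reading late-onset and influenza-like TEAEs across dose columns and against placebo. It would be too strong to say that the primary endpoint as a whole, or any safety decision in the trial, is compromised: early events are counted equally, and no decision rule uses these windows.

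**What to change.** Keep the planned tables and add:

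1. First-dose TEAE and influenza-like TEAE tables for all cohorts and placebo over one window that every cohort actually covers. One choice is through Day 106, the earliest allowed OV4 in Cohorts 1A and 1B (120 − 14), or the day before the earliest second dose if that is sooner. The alternative is through Day 120 with subjects censored at their last AE contact. A plain Day 120 cut would not do, because a 50 mg subject seen at Day 106 may not be observed beyond it.
2. Subject-days at risk or exposure-adjusted rates beside the full-window tables. For influenza-like TEAEs, also show placebo by cohort and footnote each cohort's calendar dates. Dose levels enrol in sequence and the objective concerns the flu season, so a common window alone does not remove season.
3. A SAP sentence stating where the first-dose window ends, including for subjects with no second dose. Table 1 footnote q and its copy in SAP Appendix A must be reconciled with Protocol 12.3, as must the two statements of the washout.

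The cost is SAP wording and a few tables. No new data are needed, since onset timing is already listed. The common-window table omits later events, so it supplements the full one, and placebo by cohort is only 3 subjects.
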